5. The trial design specifies that HCQ will be given for 1 year, and subjects will be followed for an additional 2 years. This approach will allow for analyses to determine if the effect of HCQ on decreasing progression to RA is apparent while subjects are on drug, and wanes when subjects are off drug. These results will inform the design of future studies.

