For the primary analysis, the test statistic will be computed using a method described by Klein (2007) [177]. Klein et al compared performance of several Wald-type chi-square statistics derived by dividing the difference of transformed Kaplan-Meier (KM) survival estimates for each arm by the associated variance derived using the delta-method. For this study, we compared the performance of the log(-log) and logit transformations (referred to as X^2_3 and X^2_5 , respectively, in Klein (2007)). The logit transformation was selected for this study, because it had slightly higher power in simulation studies. To estimate power, the test statistic was computed for 1000 simulated trials, and power was estimated as the percentage of simulated trials where the test was rejected at $\alpha=0.05$. We assumed time to failure follows an exponential distribution. As such, a 50% risk (or 50% survival) at 3 years implies the hazard per year (λ) equals 0.231 for the control arm. If the risk falls to 25% (or 75% survival) at 3 years for the treatment arm, then $\lambda = 0.096$, and the hazard ratio equals 2.4 for untreated compared to treated subjects. In a retrospective

cohort study of subjects with palindromic rheumatism, the hazard ratio (HR) for development of RA based on 3 1/3 years of follow-up was ~3 for untreated subjects compared to subjects treated with anti-malarials [112]. As such, attaining a hazard ratio of 2.4 for this study is a reasonable goal.

For example, with 80 subjects per arm, the study has 90% power to detect a reduction in risk from 50% to 25% at 3 years. Under the null case (hazard ratio=1), the test was rejected 4.6% of the time. If the risk for controls is 50%, but the HR drops to 2.1, then power is 81%. If the risk for controls is 35% and the HR remains at 2.4, then power is 77%. Given the long duration of follow-up, the sample size will be increased to 100 subjects per arm to allow for attrition of up to 20% (equally distributed across groups).

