8.3.1 Efficacy Analysis

8.3.1.1 Primary Efficacy Analysis

The primary efficacy analysis is designed to test the hypothesis that HCQ will slow or prevent the onset of clinically-apparent RA in high-risk subjects. The analysis will be based on the KM estimated risk of clinically-apparent RA at 36 months. The KM curves will be plotted along with 95% confidence intervals. The null hypothesis, “H0: survival at 3 years is equal across arms”, will be tested against the two-sided alternative with $\alpha=0.05$. The test statistic will be a Wald-type chi-square statistic derived by dividing the difference of the logit-transformed KM survival estimates for each arm by the associated variance derived using the delta-method. The logit-transformed Wald-type chi-squared statistic has better test performance than the untransformed version in that the nominal Type I error is better retained. Subjects who choose to take off-study HCQ on a continuous basis will be censored at the time this therapy begins. This analysis will ignore stratification by site and method of recruitment, because the unstratified test statistic has been shown to have better test performance [177].

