8.3.1.2 Secondary Efficacy Analyses

All secondary analyses will be conducted in an exploratory fashion with p-values and confidence intervals presented as descriptive statistics with no adjustments for multiple comparisons. Tests will be two-sided and interval estimates will be generated at the 95% confidence level. All efficacy analyses will be repeated using the PP population.

The KM estimates for the two arms will be compared using the log-rank test, and survival at 12 months will be compared using methods analogous to those described for the primary efficacy analysis. The two arms will also be compared after control of appropriate covariates using a Cox proportional hazards model. The modeling will also evaluate the relationship between time to onset of clinically-apparent RA (or IA) and covariates such as site, method of recruitment, age, sex, race, baseline characteristics, genetic and environmental factors, and biomarkers.

Treatment group comparisons of longitudinal changes in secondary efficacy endpoints, including disease activity scales, subject self-evaluation scores, and patient reported outcome scores (See Section 3.3.1, *Secondary Efficacy Endpoints*) will be evaluated using repeated measures random regression models. Models will be fit to allow piece-wise fixed-effect for time during the 12-month treatment period and during the subsequent follow-up period through 36 months. A random slope and intercept will be fit for each subject assuming an unstructured covariance matrix. Additional models may be developed to evaluate the relationship of endpoints with appropriate covariates.

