Population Level Summary: Estimated risk at 12 months for each treatment arm and the difference between the treatment arms (with 95% confidence intervals) will be derived from Kaplan-Meier (KM) curves and using the Greenwood formula for estimating the variance.	Analysis: The analysis will be based on the KM estimated risk of IA at 12 months, where risk = (1-KM estimated probability of “survival”). Survival for this analysis is defined as absence of IA. Estimated risks will be derived from a Kaplan-Meier curve using censored time-to-event data to account for attrition under the assumption of non-informative censoring. The test statistic will be a Wald-type chi-square statistic derived by dividing the difference of the logit-transformed KM survival estimates for each arm by the associated variance derived using the delta-method. (Klein, et al. 2007) [2]

8.3.3. Study Objective 4

Study Objective 4 is to evaluate the impact of a 12-month course of HCQ on the timing of development of CL-RA over the entire study period. The clinical endpoint to evaluate this objective will be the development of CL-RA through 36 months. Details on the derivation of the development of CL-RA are provided in section 8.2.1.

Table 11: Estimands of Study Objective 4

Variable: Time to development of CL-RA	
Estimand Label: Secondary 4.1	
Population: mITT	IES Policy 1
Population Level Summary: Kaplan-Meier (KM) survival curves (with 95% confidence intervals) will be estimated from baseline through Month 36 for each treatment arm.	Analysis: The analysis will be based on the KM survival curves for time to CL-RA from baseline through 36 months. Survival for this analysis is defined as absence of CL-RA. Time-to-event data are censored under the assumption of non-informative censoring. The log rank test will be used to compare HCQ vs. placebo.
Estimand Label: Secondary 4.2	
Population: mITT	IES Policy 1
Population Level Summary: Estimated hazard ratios (and 95% confidence intervals) associated with the treatment effect derived from the Cox proportional hazards model.	Analysis: A Cox proportional hazards model will be fit with covariates for site (Colorado vs. other sites) and method of recruitment, along with treatment interactions. Only interaction terms with p-values<0.05 will be retained in the model. Wald chi-square tests will be used generate p-values associated with HRs for the treatment effect. Note: The validity of the proportional hazards assumption will be evaluated.

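### No on-drug versus off-drug treatment effect is planned for time to CL-RA or IA, so waning after the drug stops can only be inferred indirectly.

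*SAP*

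**What the plan says.** Protocol 1.5.2 explains that "HCQ will be given for 1 year, and subjects will be followed for an additional 2 years", and that this allows analyses of "if the effect of HCQ on decreasing progression to RA is apparent while subjects are on drug, and wanes when subjects are off drug". The outcome named there is progression to RA, which is an event outcome.

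For timing of CL-RA (SAP 8.3.3, Table 11) and of IA (SAP 8.3.4, Table 12), the SAP plans three things:

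- Kaplan-Meier curves by arm through Month 36 with a log-rank test (Secondary 4.1 and 5.1).
- A Cox model: "A Cox proportional hazards model will be fit with covariates for site (Colorado vs. other sites) and method of recruitment", plus treatment interactions with those covariates (4.2 and 5.2). Proportional hazards is to be checked, but no consequence is stated if the check fails.
- Kaplan-Meier curves by site group and arm (4.3 and 5.3).

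None of these has a treatment-by-period term, a landmark at the end of treatment, or any other off-drug contrast. The time-varying covariates that SAP 8.3.5 allows for are symptoms and risk factors, not the treatment effect.

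Outside Objectives 4 and 5, the SAP plans risk differences with 95% CIs for CL-RA at 36 months (Primary 1.0) and 12 months (Secondary 2.1), and for IA at 12 months only (Secondary 3.1).

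For the longitudinal scores, Protocol 8.3.1.2 does split time: "Models will be fit to allow piece-wise fixed-effect for time during the 12-month treatment period and during the subsequent follow-up period". SAP Tables 14, 16 and 17 also list on-drug versus off-drug period as a candidate effect.

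**The concern.** Drug stops one third of the way through follow-up, so a hazard ratio that changes at that point is foreseeable. Protocol 1.5.2 itself cites a prevention trial in which one rituximab dose delayed RA by about 12 months without preventing it. Delay while on drug and lasting prevention are different answers, and a hazard ratio averaged over 36 months mixes them.

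The scores have a foreseen split at the end of treatment, while the event outcomes that Protocol 1.5.2 is about have none. Protocol 8.4 also counts the study a success if the secondary analysis shows a difference between the survival curves, so it matters to report how the curves differ as well as whether they do.

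**Working it through.** **Inputs from the documents.** Placebo and HCQ risks of 50% and 25% at 3 years with exponential times (Protocol 8.1); 144 randomised 1:1, taken as 72 per arm (Interim SAP 5.2.2.1); 20% loss per arm (Interim SAP 8.1); Week 52 target day 364 ± 14 (SAP 8.1.2, Table 4).

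**Assumed.** The waning and catch-up patterns, since the documents give no waning figure. Loss is taken as exponential. The Cox model has arm only.

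**Reproducing the plan's figures.** Hazards are −ln(0.50)/3 = 0.231 and −ln(0.75)/3 = 0.096 per year. Their ratio is 2.41, matching the protocol's statement that "the hazard ratio equals 2.4 for untreated compared to treated subjects"; inverted it is 0.415. The protocol states that "with 80 subjects per arm, the study has 90% power to detect a reduction in risk from 50% to 25% at 3 years". Simulating the logit-transformed Kaplan-Meier test (10,000 trials, no loss) gives 91.1%, and the delta-method formula gives 89.6%. Both agree with 90%.

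**What each planned estimate would show.** With hazard ratio a in months 0–12 and b in months 12–36:

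- Placebo risk at T years: 1 − exp(−0.231 T).
- HCQ risk at 12 months: 1 − exp(−0.231 a).
- HCQ risk at 36 months: 1 − exp(−0.231 (a + 2b)).
- HCQ risk from month 12 to 36 if event-free at month 12: 1 − exp(−0.231 × 2b).

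Example, full waning (a = 0.415, b = 1.00): the 36-month HCQ risk is 1 − exp(−0.231 × 2.415) = 42.8%.

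The single Cox HR comes from large-sample simulation with 20% loss; the risks are without censoring. Risks are percentages, placebo vs HCQ, with the difference in points in brackets.

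| Pattern (a, then b) | Single Cox HR | 12-month risk | 36-month risk | Month 12–36 risk if event-free at 12 |
|---|---|---|---|---|
| Design effect (0.415, 0.415) | 0.42 | 20.6 vs 9.1 (11.5) | 50.0 vs 25.0 (25.0) | 37.0 vs 17.5 |
| Full waning (0.415, 1.00) | 0.75 | 20.6 vs 9.1 (11.5) | 50.0 vs 42.8 (7.2) | 37.0 vs 37.0 |
| Constant weak effect (0.75, 0.75) | 0.75 | 20.6 vs 15.9 (4.7) | 50.0 vs 40.5 (9.5) | 37.0 vs 29.3 |
| Catch-up (0.42, 1.3) | 0.91 | 20.6 vs 9.2 (11.4) | 50.0 vs 50.2 (−0.2) | 37.0 vs 45.2 |

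Rows two and three share a Cox HR. The two risk differences tell them apart: the gap shrinks from 11.5 to 7.2 points in one and grows from 4.7 to 9.5 in the other. No planned output gives the last column.

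**Precision of a period split.** Under full waning with 72 per arm and 20% loss, about 60 events are expected: 21 in months 0–12 and 39 in months 12–36. The simulated 95% CI factors are ×/÷ 2.58 and ×/÷ 1.89. For the ratio of the two HRs the factor is exp(√((ln 2.58)² + (ln 1.89)²)) = exp(√(0.898 + 0.405)) = 3.1. The true ratio is 1.00/0.415 = 2.4, so a typical interval runs from 2.4/3.1 = 0.8 to 2.4 × 3.1 = 7.4 and includes 1. Power for the treatment-by-period term is about 32%, or about 66% if the on-drug HR were 0.20.

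**Where to cut.** The Week 52 window ends on day 364 + 14 = 378. A cut at day 364 would count disease found at an End of Treatment visit on days 365–378 as off-drug. Moving the cut by 14 days shifts at most about 144 × 0.231 × 14/365 = 1.3 events, so the precision figures still apply.

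**The case against.** **The plan already shows waning for CL-RA.** A reader might infer that the single hazard ratio is the only evidence on timing, or that a delay followed by catch-up would be reported as no effect. The documents do not support either. In the catch-up row, the planned 12- and 36-month risk differences would show about 11 points and then none, and the planned curves would show them converging. Those differences are also fully randomised contrasts, which an off-drug HR is not. This stands for CL-RA. It does not stand for IA, which has no 36-month difference, and it does not supply the off-drug effect itself.

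**Protocol 1.5.2 is rationale, not an objective.** Objective 4 concerns timing over the whole study, which a log-rank test and an overall HR do address. Protocol 3.3.1 defines the score endpoints by period but not the time-to-event ones, and the SAP makes the score modelling optional. This is fair and limits the weight of the point. The stated purpose of the off-drug period still has no direct estimate.

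**It is not literally one hazard ratio.** Retained site or recruitment interactions would give several. That is correct, but none would vary by time.

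**The split is imprecise.** This is correct: even complete waning would usually leave an interval for the ratio that includes no waning. The futility stop recommended after the April 2022 interim analysis (SAP 5.4) may have reduced off-drug follow-up further.

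**It comes late.** The SAP was signed in May 2023, after the interim results and the stop recommendation, so a new split needs that label.

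**Conclusion.** The point holds in a limited form. No on-drug versus off-drug effect estimate is planned for time to CL-RA or IA, although looking for waning is a stated purpose of the design. For CL-RA waning can be inferred from two planned risk differences and the curves; for IA, only from the curves and the 12-month difference. The 36-month Cox HR adds nothing on this question: about 0.75 fits both full waning and a steady weak effect.

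The numbers rest on the design's placebo hazard, 20% loss, 72 per arm and assumed waning patterns. They are for CL-RA, because the documents give no rate for IA. The actual number of off-drug events is not known from the documents. The primary analysis and its conclusion are untouched. This is a cheap improvement to descriptive secondary analyses.

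**What to change.** - **Secondary 4.2 and 5.2:** add one treatment-by-period term and report the treatment HR with 95% CI for day 1–378 and after day 378, with the ratio of the two and its CI. Split at this fixed time from randomisation, not at each participant's own drug stop. Keep the 36-month HR as a summary.
- **Proportional hazards:** state that the period-specific HRs are the reported description if the check fails.
- **Risk differences:** add a 36-month risk difference for IA, and show the 12- and 36-month differences side by side for both endpoints.
- **Optional:** Kaplan-Meier curves by randomised arm from day 378 among those event-free then.
- **Labels:** descriptive; the off-drug contrast is conditional on being event-free at day 378 and so not fully randomised; added after the interim results and the stop recommendation, and recorded in SAP section 12.

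The cost is a few lines of SAP text and code on existing data. The downside is wide intervals, roughly ×/÷ 2.6 on drug, ×/÷ 1.9 off drug and ×/÷ 3.1 for the ratio, and wider off drug if early stopping cut follow-up. A ratio whose interval includes 1 must not be read as evidence that the effect persisted.

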the absence of inflammation at baseline, van de Stadt and colleagues demonstrated that anti-CCP levels >3 times the normal cut-off level were the strongest predictive factor for development of future RA with a 2-3 year period [92]. Bos and colleagues have also shown that ~30% of subjects with anti-CCP2 positivity developed RA within ~3 years; in addition, subjects with the highest levels of anti-CCP2 had the highest rates of progression (>50%) to RA [85]. In addition, Beck and colleagues have identified in prospective follow-up of individuals identified with anti-CCP2 or anti-CCP3 positivity in absence of IA through health-fair screening that anti-CCP2 levels of >2 -3 times the normal cut-off level were associated with a 70% PPV of development of RA within 3 years [86]. Furthermore, Demourelle and colleagues have demonstrated that anti-CCP2 levels >2 times the normal cut-off level had a 55% PPV for the onset of clinically-apparent RA within 2 years [31], with additional unpublished analyses identifying that an elevation of anti-CCP3 ≥ 2 times the normal cut-off had a PPV of ~60% for future RA within 3 years. Finally, in a natural history study of initially arthritis-free FDRs of family members with RA, Ramos-Remus

In addition to predicting the overall likelihood of RA development, autoantibodies, and in particular anti-CCP can be used to predict the timing of future onset of RA – an important concept when considering a clinical trial of limited temporal duration. Supporting this, in multiple studies, anti-CCP positivity is first identified on average 3-5 years prior to the clinical onset of RA [76-78, 91]; therefore, if anti-CCP is positive, as discussed above it is highly specific for the future onset of RA, as well as highly indicative of RA within a 5-year time period. In addition, higher levels of autoantibody typically develop closer to the time of clinical appearance of RA (Figure 1.6). In particular, in a prospective study of subjects who were positive for anti-CCP in

and colleagues found that in individuals who were anti-CCP2 positive at any level (and RF negative) had a PPV of 58.3% for future onset of RA [90]. In addition, they found that over 50% of subjects who were positive for anti-CCP (+) at their baseline visit developed RA within 3 years.

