7.2. Randomization

Participants were randomized in a 1:1 ratio to either HCQ or placebo. Anticipating that some study sites would only randomize a few participants, an adaptive randomization procedure based on Pocock and Simon [1] minimization concepts was used to increase the likelihood of balance between treatment arms on key factors associated with progression to clinically-apparent RA. The factors used in the adaptive randomization procedure were smoker status (smoker vs. non-smoker), study site, and method of recruitment (i.e., first degree relative (FDR), general population, or clinic patient). Participants with elevated anti-CCP levels that met assay positivity criteria were identified for this trial through three general approaches that included the following:

- Pre-screening FDRs of patients with RA.
- Health-fair, biobank, or other population-based pre-screening.
- Identification in rheumatology clinics of participants with ACPA positivity in the absence of IA.

These three participant pools provided a sampling of the types of participants for whom this preventative approach would be applicable.

To avoid possible issues of familial correlation, our strong preference was to randomize only 1 FDR per family. Participants were asked about participation of immediate family members during the consent process and during study participation. However, recognizing operational

Autoimmunity Centers of Excellence
Statistical Analysis Plan – ARA08 StopRA

barriers to accurately track family membership and our suspicion that multiples per family would be a rare occurrence, randomization of multiple FDRs per family was allowed.

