8.1.4. Multiple Comparisons/Multiplicity

This study has a single primary analysis to be tested at $\alpha=0.05$. Consequently, no adjustments for multiplicity are needed for Type I error protection.

The secondary efficacy analyses are considered to be supportive with p-values and confidence intervals presented as descriptive measures of strength of evidence rather than formal statistical inference. Therefore, no multiplicity adjustments are needed for this study.

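### The planned adjusted Cox estimates of the HCQ effect omit baseline anti-CCP3 level; adding it would bring a modest gain in precision and protection against chance imbalance

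*SAP*

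**What the plan says.** SAP Tables 11 and 12 carry the same sentence for Secondary 4.2 and 5.2: "A Cox proportional hazards model will be fit with covariates for site (Colorado vs. other sites) and method of recruitment, along with treatment interactions". Interactions stay only at p<0.05, and the treatment hazard ratio is read from that model.

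The protocol leaves the adjustment set partly open. Section 8.3.1.2 says: "The two arms will also be compared after control of appropriate covariates using a Cox proportional hazards model". It also lists biomarkers among the covariates to be related to time to onset of RA or IA. Section 8.5.2 fixes site and recruitment method as covariates in the secondary models.

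Minimisation used smoking status, site and recruitment method (SAP 7.2). Anti-CCP3 is drawn from everyone at Baseline (Protocol 6.5.3) and tabulated by arm, in units and by category (SAP 6.2).

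On prognosis, Protocol 1.1.6 reports that in one cited prospective cohort anti-CCP "levels >3 times the normal cut-off level were the strongest predictive factor for development of future RA" over two to three years. It adds that higher levels tend to appear nearer to clinical onset.

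Anti-CCP3 is a listed candidate in Objective 6 (SAP 8.3.5), an exploratory Cox analysis of RA only. There it is screened in a model with treatment and a treatment interaction, then faces p-value selection.

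**The concern.** Objectives 4 and 5 ask about timing, and antibody level is the baseline variable that the protocol ties most closely to timing. The entry criterion of at least 40 units narrows the range but does not remove it. With a normal cut-off of 20 units, three times the cut-off is 60 units, inside the eligible range, and SAP 6.2 separates 2 to <3 times from at least 3 times the upper limit. For RA there is also a built-in link: in SAP Table 6 a result above three times the upper limit scores 3 serology points and a lower positive scores 2, towards the 6 needed.

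Two things are at stake. Leaving a prognostic covariate out of a Cox model moves a non-null hazard ratio towards 1 and costs some power, even under randomisation. And because titre was not balanced by design, neither planned model would correct a chance difference between arms.

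**Working it through.** **1. The plan's own figures.** Protocol 8.1 states that "with 80 subjects per arm, the study has 90% power to detect a reduction in risk from 50% to 25% at 3 years", and that "the hazard ratio equals 2.4 for untreated compared to treated subjects". The hazards are -ln(0.50)/3 = 0.231 and -ln(0.75)/3 = 0.0959 per year; their ratio is 2.41. Simulating the logit-transformed Kaplan-Meier test (4,000 trials, two-sided 0.05) gives:

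- 80 per arm, 50% vs 25%: 91.6% (two-proportion formula 91.2%; stated 90%)
- hazard ratio 2.1: 80.8% (stated 81%)
- control risk 35%, hazard ratio 2.4: 77.7% (stated 77%)
- null: 4.4% (stated 4.6%)
- attrition: 80/(1 - 0.20) = 100 per arm (stated 100)
- 140 participants, 20% loss, no interim: 83.4% (Protocol 8.4: 83%)

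These reproduce, and all belong to the primary test. No power is stated for the Cox models.

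**2. How prognostic is anti-CCP3?** The documents give no hazard ratio for level among people already at 40 units or more. Protocol Table 1.2 reports, from one cohort, 27% with IA at a median of 11 months among all anti-CCP positives, and 50% with RA in about 12 months at higher titres. The ratio of cumulative hazards is ln(0.50)/ln(0.73) = 0.693/0.315 = 2.2. This is only a guide: the endpoints and times differ, the comparison group includes the high titres, and the titre range is wider than in this trial. A range is therefore needed.

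**3. Effect of leaving it out.** Inputs: 144 randomised (interim SAP 5.2.2.1), 1:1, 20% loss (interim SAP Appendix 8.1), 36 months, placebo risk 50%, true conditional hazard ratio 1/2.4 = 0.417, about 50 events; 3,000 trials per row. Site and recruitment method were not simulated.

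| Assumed anti-CCP3 effect | HR without it | Power without → with | Gain (points) |
|---|---|---|---|
| High vs lower, HR 1.5 (half high) | 0.42 | 84.6% → 84.7% | 0.1 |
| HR 2 (half high) | 0.42 | 84.1% → 85.8% | 1.7 |
| HR 2 (80% high) | 0.42 | 83.7% → 84.9% | 1.2 |
| HR 2.2 (half high) | 0.43 | 82.8% → 85.4% | 2.6 |
| HR 3 (half high) | 0.44 | 82.1% → 86.0% | 3.9 |
| HR 4 (half high) | 0.45 | 78.3% → 85.1% | 6.8 |
| HR 1.5 per SD | 0.42 | 82.1% → 84.3% | 2.2 |
| HR 2 per SD | 0.45 | 77.7% → 85.4% | 7.7 |
| HR 3 per SD | 0.51 | 68.7% → 86.5% | 17.8 |

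A separate simulation (1,500 trials per cell, true hazard ratio 0.415) gave 88% → 90% at 1.4 per SD, 79% → 85% at 1.7 and 77% → 83% at 2.0: the same direction and order of size.

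**4. Chance imbalance.** With 72 per arm, the standard error of the between-arm difference in mean log titre is sqrt(2/72) = 0.167 SD. A two-standard-error difference is 0.333 SD. It would multiply or divide the estimated hazard ratio by 1.5^0.333 = 1.14, or by 2^0.333 = 1.26, for titre hazard ratios of 1.5 or 2 per SD.

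**The case against.** **Nothing decisive depends on these models.** SAP 8.1.4 makes secondary p-values descriptive, and power is claimed only for the 36-month Kaplan-Meier comparison. This stands.

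**The shift is not bias.** A reader might infer that the planned hazard ratio is wrong. It is not: the shift is non-collapsibility. The ratio without titre is a valid marginal quantity, stays at 1 under no effect, and matches the design value of 2.4, itself derived from marginal risks of 50% and 25%. Since the DSMB recommended stopping for futility (SAP 5.4), there may be little effect to attenuate; protection against imbalance would then be the main benefit. This stands.

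**Objective 6 already fits treatment with anti-CCP3.** For RA it does, always at the screening step, and a strong effect would seldom be dropped. With 50 events the standard error per SD is about 1/sqrt(50) = 0.141. At 1.7 per SD, z is 0.531/0.141 = 3.8, and retention at p<0.1 is about 98%. So the SAP does not ignore titre for RA. But the screening model carries an interaction, so its treatment coefficient refers to one titre value rather than to an overall effect; the final model is conditional on selection; and IA has no counterpart. SAP section 12 does not list the narrowing to RA as a change from Protocol 8.3.1.2.

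**Protocol 8.5.1 allows adjustment for imbalanced factors.** It only permits it. Choosing after seeing the baseline table by arm, with assignments to be unmasked before database lock (SAP 5.4), is less credible than fixing the covariate now.

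**The SAP follows the protocol on site and recruitment.** True. Protocol 3.1.1 names smoking, site and recruitment as its key factors. The point is an addition to the planned models, not a departure from the protocol.

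**Conclusion.** The point holds as a minor one about secondary, descriptive estimates. Secondary 4.2 and 5.2 omit a baseline variable that the protocol's own background treats as prognostic. For IA no planned model contains it; for RA only exploratory screening and selection models do.

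The gain from including it is about 0 to 3 power points at moderate strength (a two-group hazard ratio up to about 2.2, or 1.5 per SD) and about 8 points at 2 per SD. The 18-point figure needs 3 per SD, which nothing in the documents supports. All sizes rest on an assumed prognostic effect, a true conditional hazard ratio near 0.42 and full 36-month follow-up.

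Two further readings are not supported. The trial has not lost stated power: the primary test is a Kaplan-Meier comparison that these models do not touch. And the protocol does not itself rank anti-CCP3 level as the strongest predictor in this population. The phrase reports one cited cohort, for anti-CCP above three times the cut-off among anti-CCP positives, not for anti-CCP3 among people all at 40 units or more.

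**What to change.** In SAP 8.3.3 and 8.3.4, add a version of Secondary 4.2 and of 5.2 with baseline log(anti-CCP3) as a fixed covariate, retained whatever its p-value, alongside site and recruitment method. Report each beside the planned model, and describe the two hazard ratios as conditional on titre and not conditional on titre, so that a difference is not read as bias.

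Label the added models supportive and record them in SAP section 12. The SAP was signed in May 2023, after the April 2022 interim results and the DSMB's recommendation to stop and release treatment assignments, so they cannot be presented as planned before any unmasked look at the data.

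The cost is one variable already in the baseline dataset and one extra parameter against about 50 events expected under the design assumptions. The gain is greatest for IA, where no titre-adjusted estimate is otherwise planned.
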